4.3. Protocol Deviations

Subjects who did not meet the eligibility criteria for study entry but enrolled in the study, will be summarized. The summary will present the number and percentage of subjects who did not meet at least 1 eligibility criterion and the number of subjects who did not meet specific criteria based on the All Enrolled Analysis Set. A by-subject listing will be provided for those subjects who did not meet at least 1 eligibility (inclusion or exclusion) criterion. The listing will present the eligibility criterion (or criteria if more than 1 deviation) that subjects did not meet and related comments, if collected.

Protocol deviations occurring after subjects entered the study are documented during routine monitoring. The number and percentage of subjects with important protocol deviations by deviation category (eg, nonadherence to study drug, violation of select inclusion/exclusion criteria) will be summarized for the All Enrolled Analysis Set.

4.4. Assessment of COVID-19 Impact

This study was ongoing during the novel coronavirus (2019 nCOV [COVID-19]) pandemic which has caused a disruption in the regular visit schedules for this study. Some subjects were unable to attend onsite visits due to shelter in place guidelines, site closures, or other reasons. This section provides how to handle special situations due to COVID-19 in the analysis.

Adverse events due to COVID-19 will be included in AE analyses if applicable.

4.4.1. Study Drug or Study Discontinuation Due to COVID-19

A by-subject listing of reasons for premature study drug or study discontinuation due to COVID-19 will be created for the enrolled analysis set.

4.4.2. Protocol Deviations Due to COVID-19

Similar summary as described in protocol deviations section will be performed for important protocol deviations due to COVID-19 for the enrolled analysis set.

A by-subject listing will be provided for subjects with important protocol deviation related to COVID-19. A separate listing will be provided for subjects with non-important protocol deviation related to COVID-19.

4.4.3. Missed and Virtual Visits due to COVID-19

A by-subject listing of subjects with missed or virtual visits due to COVID-19 will be provided by subject ID number in ascending order.

Information regarding missed or virtual visits due to COVID-19 was collected as free text in the CRF comment fields. The determination of missing or virtual visits due to COVID-19 was done using Natural Language Processing (NLP) to search the CRF comment fields. A brief description of the natural language processing algorithm developed for determining missed and virtual visits based on CRF comment text is provided in Appendix 2.

5. BASELINE CHARACTERISTICS

5.1. Demographics

Subject demographic variables (i.e. age, sex, race, and ethnicity) will be summarized by HCV genotype (GT1, GT1 broken down [1a, 1b], GT2, GT2 broken down [GT2a/2c, GT2b], non-GT1) and overall using descriptive statistics (n, mean, SD, median, Q1, Q3, minimum, and maximum) for age and BMI (kg/m²), and using the numbers and percentages of subjects for age categories (< 65 years, \geq 65 years), BMI categories (< 25 kg/m², \geq 25 kg/m²), sex, race, and ethnicity. Age is calculated in years at the date of initial study drug administration. If a subject did not receive study drug after enrollment, the subject's age will be calculated from the date that the subject signed the informed consent form. The summary of demographic data will be provided for the Safety Analysis Set.

A by-subject demographic listing, which includes the date the informed consent was signed, will be provided by subject ID number in ascending order.

5.2. Other Baseline Characteristics

Other baseline characteristics include:

- body mass index (BMI; in kg/m²) as a continuous variable and as categories (< 25 kg/m², ≥ 25kg/m²)
- HCV genotype/subgenotype (GT1 with GT1 broken down as GT1a and GT1b; non-GT1 with non-GT1 broken down as GT2, GT2a/2c and GT2b)
- IL28B (CC, non-CC; with non-CC further broken down to CT, TT)
- baseline HCV RNA (log_{10} IU/mL) as a continuous variable and as categories (< 800,000 IU/mL, $\geq 800,000$ IU/mL)
- baseline ALT (U/L) as a continuous variable and as categories ($\leq 1.5 \times \text{ULN}$, $> 1.5 \times \text{ULN}$)
- prior HCV treatment experience (treatment naive, treatment experienced)
- prior HCV treatment response (non-responder, relapse/breakthrough, early treatment discontinuation, met a virologic stopping rule, unknown) for treatment experienced subjects
- prior HCV treatment for treatment experienced subjects (Peg-IFN, Other)
- estimated glomerular filtration rate (eGFR) using the Cockcroft-Gault equation
 - eGFRcg (mL/min) = $[(140 age (yrs)) \times weight (kg) \times (0.85 \text{ if female})] / (serum creatinine (mg/dL) \times 72)$, where weight is total body mass in kilograms.

These baseline characteristics will be summarized by HCV genotype (GT1 with GT1 broken down as GT1a and GT1b; non-GT1 with non-GT1 broken down as GT2, GT2a/2c and GT2b) and the study overall using descriptive statistics (n, mean, SD, median, Q1, Q3, minimum, and maximum) for continuous variables and using the numbers and percentages of subjects for categorical variables. The summary of baseline characteristics will be provided for the Safety Analysis Set.

A by-subject listing of other baseline characteristics will be provided by subject ID number in ascending order. The type of assay used to determine the HCV genotype will also be displayed in this listing.

A separate by-subject data listing for cirrhosis determination will be provided for safety analysis set

A separate by-subject data listing for prior HCV treatment and response will be provided for all subjects. The listing will display the prior HCV treatment experience for all subjects as well as the prior HCV regimen, the treatment duration, and the prior HCV treatment response for treatment experienced subjects.

5.3. Medical History

General medical history data will be collected at screening and a by-subject listing will be provided for the Safety Analysis Set.

6. EFFICACY ANALYSES

6.1. Primary Efficacy Endpoint

6.1.1. Definition of the Primary Efficacy Endpoint

The primary efficacy endpoint is SVR12 defined as HCV RNA < LLOQ 12 weeks after discontinuation of study drug in the FAS. The COBAS® AmpliPrep/COBAS® TaqMan® HCV Quantitative Test, v2.0 will be used to measure HCV RNA. The LLOQ for this assay is 15 IU/mL.

6.1.2. Statistical Hypothesis for the Primary Efficacy Endpoint

In the primary efficacy analysis, the SVR12 rate in FAS will be compared to the pre-specified efficacy threshold of 78% using a 2-sided exact 1-sample binomial test at the 0.05 significance level. The null (H0) and alternative (H1) hypotheses used to assess the superiority of SOF/VEL relative to the performance goal of 78% as follows:

H0: SVR12 rate = 78%

H1: SVR12 rate \neq 78%

In addition, a point estimate with a 2-sided 95% exact confidence interval (CI) using the binomial distribution (Clopper-Pearson method) {Clopper 1934} will be constructed for the SVR12 rate.

6.1.3. Primary Analysis of the Primary Efficacy Endpoint

The 2-sided 1-sample binomial test will be used to test the statistical hypothesis described above. The 2-sided 95% exact CI based on the Clopper-Pearson method will be provided for the SVR12 rate

6.1.4. Subgroup Analysis of the Primary Efficacy Endpoint

The point estimates and the 2-sided 95% exact CIs of the SVR12 rates will be displayed by genotype (GT1 with GT1 broken down as GT1a and GT1b; non-GT1 with non-GT1 broken down as GT2, GT2a/2c and GT2b) for each subgroup outlined in Section 3.3.

The SVR rates will be summarized by categories of early viral response to explore possible early on-treatment predictors of SVR12. The relationship between SVR12 and study drug interruption may also be explored.

A Forest plot will graphically present the point estimates and the 2-sided 95% exact CIs of the SVR12 rates by HCV genotype for each of the subgroups.

6.2. Secondary Efficacy Endpoints

6.2.1. Definition of Secondary Efficacy Endpoints

Secondary efficacy endpoints include the following:

- The proportion of subjects who attain HCV RNA < LLOQ at 4 and 24 weeks after cessation of treatment (SVR4 and SVR24)
- The proportion of subjects with virologic failure as the following:
 - On-treatment virologic failure
 - HCV RNA ≥ LLOQ after having previously had HCV RNA < LLOQ, while on treatment, confirmed with 2 consecutive values (note, second confirmation value can be posttreatment), or last available on-treatment measurement with no subsequent follow up values (ie, breakthrough)
 - > 1 log₁₀ IL/mL increase in HCV RNA from nadir while on treatment, confirmed with 2 consecutive values (note, second conformation value can be posttreatment), or last available on-treatment measurement with no subsequent follow up values (ie, rebound)
 - \circ HCV RNA persistently \geq LLOQ through 8 weeks of treatment (ie, nonresponse)

— Relapse

O HCV RNA ≥ LLOQ during the posttreatment period having achieved HCV RNA
 < LLOQ at EOT, confirmed with 2 consecutive values or last available posttreatment measurement

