3.4.2. Virologic Response-Based Treatment Stopping Criteria

The following on-treatment Virologic Response-based Treatment Stopping Criteria will be utilized:

- Confirmed HCV RNA ≥ LLOQ after 2 consecutive HCV RNA < LLOQ
- Confirmed > 1 log₁₀ increase in HCV RNA from nadir
- HCV RNA \geq LLOQ through 8 weeks of treatment

Confirmation, when required, should be performed as soon as possible and must occur no later than 2 weeks after an initial observation indicating virologic failure during the on-treatment phase.

Subjects who terminate study drug early due to virologic failure as defined above will complete the Early Termination (ET) visit and all posttreatment visits.

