6.2.2. Analysis Methods for Secondary Efficacy Endpoints

[figure not shown]
For analyses of SVR4 and SVR24, subjects will be assigned a value at each visit based on the analysis visit windows specified in Section 3.7.2. Missing values will be imputed based on the categorical imputation rules described in Section 3.5.1. The 2-sided 95% exact CI based on Clopper-Pearson method will be provided for the proportion of subjects who attain SVR4 and SVR24 by HCV genotype (GT1 with GT1 broken down as GT1a and GT1b; non-GT1 with non-GT1 broken down as GT2, GT2a/2c and GT2b). The overall category for "HCV RNA < LLOQ" will be split into the following 2 subcategories: "< LLOQ TND" for subjects with target not detected and "< LLOQ detected" for subjects with < LLOQ in tabular displays.

For the virologic failure analysis, a summary table of the number and percentage of subjects with SVR12, virologic failure, and Other will be created. This summary will be performed broken down by HCV genotype (GT1 with GT1 broken down as GT1a and GT1b; non-GT1 with non-GT1 broken down as GT2, GT2a/2c and GT2b). All subjects who achieve SVR12 will be categorized as SVR12. Virologic failure will be descriptively summarized as "on-treatment virologic failure" and relapse (which will be broken down by study drug completed yes/no).

Subjects who do not achieve SVR12 and do not meet criteria for virologic failure will be categorized as "Other." The denominator for relapse will be the number of subjects who had HCV RNA < LLOQ on their last observed on-treatment HCV RNA measurement; otherwise, the denominator will be the number of subjects in the FAS. Virologic outcomes will also be provided by prior HCV treatment experience on FAS overall and by HCV genotype.

A concordance table between SVR12 and SVR24 will be provided by HCV genotype (GT1 with GT1 broken down as GT1a and GT1b; non-GT1 with non-GT1 broken down as GT2, GT2a/2c and GT2b) and overall on FAS who had observed HCV RNA measurements at both posttreatment Week 12 and posttreatment Week 24 visits.

In addition, a summary table of the number and percentage of subjects with HCV RNA < LLOQ and ≥ LLOQ at the posttreatment follow-up visit (observed and imputed, with reasons for imputed) will be provided for each posttreatment follow-up visit overall and by HCV genotype. The 2-sided 95% Clopper-Pearson exact CIs will be presented for the overall proportion of subjects with HCV RNA < LLOQ.

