6.4. Changes from Protocol-specified Efficacy Analyses

There are no planned changes from protocol-specified efficacy analyses.

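### SAP 6.2.1 ties relapse to a < LLOQ end-of-treatment value, so one pattern of confirmed posttreatment viraemia is counted as 'Other' instead of virologic failure

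*SAP*

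**What the plan says.** The proportion with virologic failure is a secondary endpoint (Protocol 8.1.3). SAP 6.2.1 builds it from four definitions.

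- **Breakthrough:** "HCV RNA ≥ LLOQ after having previously had HCV RNA < LLOQ, while on treatment, confirmed with 2 consecutive values". The second value may be posttreatment. A last on-treatment value counts without confirmation only if nothing follows it.
- **Rebound:** a rise of more than 1 log10 from nadir on treatment, confirmed in the same way.
- **Nonresponse:** persistently ≥ LLOQ through 8 weeks of treatment.
- **Relapse:** posttreatment HCV RNA ≥ LLOQ after HCV RNA "< LLOQ at EOT, confirmed with 2 consecutive values or last available posttreatment measurement".

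SAP 6.2.2 then tabulates SVR12, virologic failure and a residual row: "Subjects who do not achieve SVR12 and do not meet criteria for virologic failure will be categorized as" 'Other'. SVR12 takes precedence over everything else. No order is given between on-treatment failure and relapse. The relapse denominator is limited to subjects whose last observed on-treatment value was < LLOQ; all other rows use the FAS. The SAP does not define EOT for HCV RNA. The only end-of-treatment rule in SAP 3.7.2 is in the ECG table note.

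**The concern.** A residual row should hold subjects who failed for non-virologic reasons or have missing data. Relapse depends on one sample, the end-of-treatment value, and breakthrough depends on the value immediately after it. If the end-of-treatment sample is ≥ LLOQ and the next is < LLOQ, both definitions are closed to that subject, whatever happens later. A subject with repeated quantifiable virus after treatment then leaves the virologic-failure count, and the secondary endpoint looks better than the data.

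**Working it through.** **Inputs.** LLOQ is 15 IU/mL and lower values are set to 14 (SAP 3.6). HCV RNA is taken at Weeks 2, 4, 8 and 12 and at posttreatment Weeks 4, 12 and 24 (Protocol Appendix 2). Values up to last dose + 3 days are on-treatment (SAP 3.7.2). N is about 36 and expected SVR12 is 96% (SAP 1.3). The plan gives no figure for virologic failure. Its one design figure, power above 80%, reproduces: 82.7% if the two-sided p is twice the tail (success at 34/36 or more), 94.5% by the minimum-likelihood method (33/36 or more). Nothing below depends on the power.

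**Step 1: the pattern.** Week 8 < LLOQ; Week 12 = 20 IU/mL (illustrative); posttreatment Week 4 < LLOQ; posttreatment Weeks 12 and 24 ≥ LLOQ.

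| Definition | Result |
|---|---|
| SVR12 | No: Week 12 posttreatment is ≥ LLOQ |
| Breakthrough | No: the next value is < LLOQ, and follow-up values exist |
| Rebound | No: log10(20/14) = 0.155, below 1. A larger value would not be confirmed either, because the next value is 14, so log10(14/14) = 0 |
| Nonresponse | No: Week 8 is < LLOQ |
| Relapse | No: the end-of-treatment value is ≥ LLOQ |
| SAP 6.2.2 row | 'Other' |

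**Step 2: how wide the gap is.** The definitions were applied to every < LLOQ / ≥ LLOQ sequence. The assumptions were that no rebound is triggered, EOT is the last on-treatment value, and SVR12 overrides failure. For subjects who complete Week 12 with that value ≥ LLOQ, Weeks 2, 4 and 8 give 2³ = 8 patterns.

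- All posttreatment values ≥ LLOQ: 7 breakthrough, 1 nonresponse, 0 'Other'.
- Posttreatment Week 4 < LLOQ, then Weeks 12 and 24 ≥ LLOQ: 3 breakthrough, 1 nonresponse, 4 'Other'. The four are exactly those with Week 8 < LLOQ.

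**Step 3: a second route to 'Other'.** A subject who stops before Week 8, was never < LLOQ, has no rise above 1 log10 and is ≥ LLOQ throughout follow-up meets no definition. The SAP does not say whether that is intended.

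**Step 4: overlap.** Weeks 2, 4 and 8 ≥ LLOQ, end of treatment < LLOQ, then posttreatment ≥ LLOQ meets nonresponse and relapse. Week 2 < LLOQ, Weeks 4 and 8 ≥ LLOQ, Week 12 < LLOQ, then posttreatment ≥ LLOQ meets breakthrough and relapse. Each such subject is one virologic failure but fits two sub-rows, which have different denominators.

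**Step 5: size.** One subject is 1/36 = 2.8 points. Expected non-SVR12 subjects: 36 × (1 − 0.96) = 1.44. The probability of two or fewer is 82.7%, the same binomial tail as 34 or more responders.

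**The case against.** The strongest reply is that the definitions already catch the ordinary case. Because the confirming value may be posttreatment, an end-of-treatment value ≥ LLOQ followed directly by a posttreatment value ≥ LLOQ is breakthrough, or nonresponse if the subject was never < LLOQ through Week 8. Step 2 confirms this. A reader might infer that any posttreatment failure after a ≥ LLOQ end-of-treatment value is lost; the documents do not support that. The gap needs an intervening < LLOQ value at posttreatment Week 4 (or the early-stop route in Step 3).

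The top-level table is also exhaustive and exclusive, since 'Other' takes the remainder. The fault is in what falls into that remainder.

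A reader might infer that the overlap inflates or doubles the failure count. It does not: the endpoint counts subjects, so the overlap touches only the sub-rows. Nor does a single Week 8 value ≥ LLOQ followed by Week 12 < LLOQ count as breakthrough on the scheduled visits; an extra confirming sample would be needed.

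Finally, Protocol 3.4.2 requires "Confirmed HCV RNA ≥ LLOQ after 2 consecutive HCV RNA < LLOQ", while SAP breakthrough requires one earlier < LLOQ value, and SAP 6.4 says "There are no planned changes from protocol-specified efficacy analyses". A reader might call that statement false. Protocol 3.4 does refer to 3.4.2 as defining virologic failure, but within a list of reasons to stop study drug. Section 3.4.2 has no relapse criterion, so it cannot be the full endpoint definition, and Protocol 8.5.2 leaves efficacy detail to the SAP. No error in SAP 6.4 is shown.

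It is also fair that the endpoint is descriptive, and that listings and the by-visit posttreatment table would expose an odd case among about 36 subjects. That limits the harm but does not correct the reported proportion.

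**Conclusion.** The concern holds in a narrow form. Applied literally, SAP 6.2.1 and 6.2.2 send a subject with an unconfirmed ≥ LLOQ last on-treatment value, a < LLOQ value at posttreatment Week 4 and ≥ LLOQ values at Weeks 12 and 24 to 'Other'. Virologic failure is then understated by 2.8 points per subject, assuming an FAS of 36: nothing if no such subject occurs, 5.6 points (2/36) if two do. With one or two non-SVR12 subjects likely, a single case could remove half or all of the reported failures.

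The documents give no frequency. The pattern needs viraemia at the end of treatment that drops below LLOQ and then returns, so it is expected to be uncommon. The finding assumes that EOT means the last observed on-treatment value, which agrees with the relapse denominator in SAP 6.2.2. SVR12 and the only hypothesis test are unaffected, because these subjects are non-SVR12 under any label. This is a minor correction, worth making before the SVR12 data are finalised.

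**What to change.** **SAP 6.2.1.** Define EOT for HCV RNA as the last observed on-treatment value. Count as relapse any non-SVR12 subject not classed as on-treatment virologic failure whose posttreatment HCV RNA is ≥ LLOQ (two consecutive values, or the last available) after a < LLOQ value at EOT or at any posttreatment visit.

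**SAP 6.2.2.** Extend the relapse denominator to include subjects who first qualify through a posttreatment < LLOQ value; otherwise they would enter the numerator but not the denominator. Assign each non-SVR12 subject to one row, in the order on-treatment failure, relapse, Other. State whether a subject who stops before Week 8, was never < LLOQ and is viraemic posttreatment is meant to be 'Other', since the new relapse wording does not reach that case.

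**Optional.** A note that SAP breakthrough is wider than the Protocol 3.4.2 stopping criterion would help readers. The stopping rule itself is not in question.

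The cost is a few sentences and minor programming, with no new data. The reported failure proportion may become slightly less favourable.

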6.2.2. Analysis Methods for Secondary Efficacy Endpoints

[figure not shown]
For analyses of SVR4 and SVR24, subjects will be assigned a value at each visit based on the analysis visit windows specified in Section 3.7.2. Missing values will be imputed based on the categorical imputation rules described in Section 3.5.1. The 2-sided 95% exact CI based on Clopper-Pearson method will be provided for the proportion of subjects who attain SVR4 and SVR24 by HCV genotype (GT1 with GT1 broken down as GT1a and GT1b; non-GT1 with non-GT1 broken down as GT2, GT2a/2c and GT2b). The overall category for "HCV RNA < LLOQ" will be split into the following 2 subcategories: "< LLOQ TND" for subjects with target not detected and "< LLOQ detected" for subjects with < LLOQ in tabular displays.

For the virologic failure analysis, a summary table of the number and percentage of subjects with SVR12, virologic failure, and Other will be created. This summary will be performed broken down by HCV genotype (GT1 with GT1 broken down as GT1a and GT1b; non-GT1 with non-GT1 broken down as GT2, GT2a/2c and GT2b). All subjects who achieve SVR12 will be categorized as SVR12. Virologic failure will be descriptively summarized as "on-treatment virologic failure" and relapse (which will be broken down by study drug completed yes/no).

Subjects who do not achieve SVR12 and do not meet criteria for virologic failure will be categorized as "Other." The denominator for relapse will be the number of subjects who had HCV RNA < LLOQ on their last observed on-treatment HCV RNA measurement; otherwise, the denominator will be the number of subjects in the FAS. Virologic outcomes will also be provided by prior HCV treatment experience on FAS overall and by HCV genotype.

A concordance table between SVR12 and SVR24 will be provided by HCV genotype (GT1 with GT1 broken down as GT1a and GT1b; non-GT1 with non-GT1 broken down as GT2, GT2a/2c and GT2b) and overall on FAS who had observed HCV RNA measurements at both posttreatment Week 12 and posttreatment Week 24 visits.

In addition, a summary table of the number and percentage of subjects with HCV RNA < LLOQ and ≥ LLOQ at the posttreatment follow-up visit (observed and imputed, with reasons for imputed) will be provided for each posttreatment follow-up visit overall and by HCV genotype. The 2-sided 95% Clopper-Pearson exact CIs will be presented for the overall proportion of subjects with HCV RNA < LLOQ.

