1.2. Study Design

This is a multicenter, open-label study evaluating efficacy and safety of SOF/VEL FDC in subjects with chronic HCV infection and compensated cirrhosis.

Subjects may have HCV of any genotype. Based on the HCV genotype (GT) distribution in Japan, it is expected that approximately 70% of subjects will be GT1, and approximately 30% of subjects will be non-GT1. Subjects may be either treatment-naive or treatment-experienced with interferon (IFN)-based treatments.

Approximately 36 subjects will be enrolled to be treated with SOF/VEL FDC for 12 weeks.

The total time to complete all study visits is approximately 40 weeks (42 weeks for those requiring an extension of the Screening period):

- 28 days (4 weeks) screening period [up to 42 days (6 weeks) for extenuating circumstances may be granted]
- 12 weeks study treatment period
- 24 weeks posttreatment period

The schedule of assessment is provided as an appendix to the SAP (Appendix 1).

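### A relapse first found at posttreatment Week 24 in a subject with SVR12 meets the SAP's relapse definition but is left out of its virologic-failure count at the final analysis

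*SAP*

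**What the plan says.** Virologic failure is a secondary endpoint in Protocol 8.1.3, which sets no time limit, and in SAP 6.2.1.

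- **Definition (SAP 6.2.1).** Relapse is "HCV RNA ≥ LLOQ during the posttreatment period having achieved HCV RNA" below LLOQ at end of treatment, "confirmed with 2 consecutive values or last available posttreatment measurement". SAP 1.2 describes a "24 weeks posttreatment period".
- **Reporting (SAP 6.2.2).** Subjects are tabulated as SVR12, virologic failure or Other, and virologic failure is split into on-treatment failure and relapse. The precedence rule is "All subjects who achieve SVR12 will be categorized as SVR12". The residual rule is "Subjects who do not achieve SVR12 and do not meet criteria for virologic failure will be categorized as" Other. On the breakdown: "This summary will be performed broken down by HCV genotype".
- **Denominator (SAP 6.2.2).** "The denominator for relapse will be the number of subjects who had HCV RNA < LLOQ on their last observed" on-treatment measurement. Subjects with SVR12 are not removed from it.
- **Timing.** The Week 12 analysis uses data through the posttreatment Week 12 visit (SAP 2.2.1). The final analysis follows study completion (SAP 2.3) and has no classification rule of its own. SAP 6.4 declares no change from the protocol's efficacy analyses.

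**The concern.** The definition and the table cover different periods. The definition runs to posttreatment Week 24, but the table fixes a subject's row once SVR12 is reached. A relapse after SVR12 then satisfies the endpoint's definition and cannot enter its numerator.

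At stake is a named secondary endpoint whose reported value could fall below what its own definition gives. A report could show no relapses beside an SVR24 failure and leave the reader to reconcile the two. No hypothesis test or success criterion uses this count.

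**Working it through.** The plan gives no figure for late relapse to reproduce. Its one design figure, power above 80% with 36 subjects, does reproduce: the doubled-tail exact test rejects at 34/36 or more, with power 82.7%. Nothing below depends on it.

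**Inputs.** HCV RNA windows (SAP 3.7.2, Table 2): FU-12 is days 70–146 and FU-24 is days 147–210. The scheduled Week 24 visit, 168 ± 5 = days 163–173, falls in FU-24. Missing values follow SAP 3.5.1: a missing FU-12 counts as below LLOQ only if the values on both sides are below LLOQ.

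**One case.** Last on-treatment value below LLOQ; FU-12 below LLOQ; FU-24 at or above LLOQ with no later value.

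- Relapse under 6.2.1: yes.
- In the relapse denominator: yes.
- Row in the 6.2.2 table: SVR12.
- Contribution to the relapse or virologic-failure count: 0.

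**All patterns.** Take a subject below LLOQ at end of treatment, with one record or none at each follow-up visit: n = below LLOQ, p = at or above LLOQ, m = missing. Relapse requires two consecutive available p values, or p as the last available value. There are 3 × 3 × 3 = 27 patterns. VF is the virologic-failure row, and an asterisk marks a relapse placed in the SVR12 row.

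| FU-4, FU-12 | FU-24 = n | FU-24 = p | FU-24 = m |
|---|---|---|---|
| n, n | SVR12 | SVR12* | SVR12 |
| p, n | SVR12 | SVR12* | SVR12 |
| m, n | SVR12 | SVR12* | SVR12 |
| n, p | Other | VF | VF |
| p, p | VF | VF | VF |
| m, p | Other | VF | VF |
| n, m | SVR12 | VF | Other |
| p, m | Other | VF | VF |
| m, m | SVR12 | VF | Other |

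Counted relapses: 2 + 3 + 2 + 1 + 2 + 1 = 11. Uncounted: 3. Total meeting 6.2.1: 14. These are combinations of results, not probabilities.

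The table is not a pure Week 12 snapshot either. In 5 of the 6 lines without an observed FU-12 below LLOQ (all but p, p), the FU-24 result changes the row. In the 3 lines with FU-12 below LLOQ, it never does.

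**Size.** One case overall: 1/36 = 2.8 points. Expected genotype split: 0.70 × 36 = 25.2 and 0.30 × 36 = 10.8, so about 25 and 11 subjects. One case is then 1/25 = 4.0 points in GT1 or 1/11 = 9.1 points in non-GT1.

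As an illustration, assume all 36 subjects are below LLOQ at the last on-treatment value, all reach SVR12, and k relapse first at FU-24 (Clopper-Pearson 95% intervals):

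| k (assumed) | Relapse by 6.2.2 | Relapse by 6.2.1 | SVR24 |
|---|---|---|---|
| 0 | 0/36 (0–9.7%) | 0/36 (0–9.7%) | 100% |
| 1 | 0/36 | 2.8% (0.07–14.5%) | 97.2% |
| 2 | 0/36 | 5.6% (0.7–18.7%) | 94.4% |
| 3 | 0/36 | 8.3% (1.8–22.5%) | 91.7% |

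**The case against.** The precedence rule is explicit and prespecified, and a table anchored on the primary endpoint is a reasonable design. Late relapse is not hidden. It is an SVR24 failure, it appears in the by-visit table, and SAP 6.2.2 plans a concordance table on "FAS who had observed HCV RNA measurements at both posttreatment Week 12 and posttreatment Week 24 visits". In all three uncounted patterns both visits are observed. On the one-record-per-visit model, the concordance cell for SVR12 achieved and SVR24 not achieved therefore equals the number of uncounted relapses. Protocol 8.5.2 also promises listings for virologic failure. Both documents justify their SVR24 imputation by the high correlation between SVR12 and SVR24, which suggests few such cases. The sizes above are simply the weight of one subject.

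All of that stands, and it limits the importance of the point. It does not remove the mismatch, because none of those outputs counts the case as relapse or virologic failure. Nor can the overall SVR24 failure count stand in for it: that count can include subjects without SVR12 whose missing Week 24 value is imputed as failure. If a Week 12 limit on relapse was intended, 6.2.1 does not say so.

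**Conclusion.** The concern holds. As written, SAP 6.2.2 would undercount virologic failure against SAP 6.2.1 by one for each relapse first found in the FU-24 window after SVR12: 2.8 points overall per case, and about 4.0 or 9.1 points within genotype. The effect is conditional on such a relapse, and the documents give no rate for it. The primary analysis is unaffected.

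The conclusion assumes three things:

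- The Week 24 value is confirmed or is the last available one. A value at or above LLOQ followed by a retest below LLOQ is not a relapse under 6.2.1.
- The last on-treatment value was below LLOQ.
- The three rows are exclusive. The SAP does not use that word, but the precedence sentence and the residual category imply it.

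The finding covers the 6.2.2 outputs only; SAP 6.3 is redacted.

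**What to change.** In SAP 6.2.2, keep the three-way table and say that SVR12 takes precedence in it. For the final analysis:

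1. Split the SVR12 row into subjects with SVR12 maintained or no later relapse observed, and subjects with relapse after SVR12.
2. Report the number and percentage meeting the 6.2.1 virologic-failure definition through posttreatment Week 24, with relapse after SVR12 in the relapse numerator.

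Limiting relapse in 6.2.1 to posttreatment Week 12 would also remove the contradiction, but it would narrow an endpoint to which the protocol sets no time limit.

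The cost is SAP wording and one or two table lines, with no new data. The failure rate may look slightly less favourable, and the two totals need clear labels. If the SAP is already final, its Section 1 calls for the change to be documented in the study report.
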